8.7.3 Antibody Formation

Serum samples will be tested for the presence of antibodies to botulinum toxin using an Anti Drug Antibody (ADA) assay; initially only the last sample obtained from each study subject will be analyzed together with the pre-dose baseline sample. If a sample tests positive for anti-drug antibodies, the other samples from the subject will be analyzed to determine when antibodies developed. Serum samples which test positive for binding antibodies will subsequently be tested for neutralizing activity. Blood serum for ADA tests will be collected at screening, at the visit 4 weeks after treatment and at the end of cycle visit for each treatment cycle.

The presence of antibodies will be summarized by counts and percentages of subjects by treatment group and time point. For the subgroup of subjects with a sample test positive for anti-drug antibodies, all analyzed samples will be analyzed descriptively by counts over time as well.

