11.15.2 Antibody Test

Serum samples will be tested for the presence of antibodies to botulinum toxin using an Anti Drug Antibody (ADA) ELISA assay; initially only the last sample obtained from each study subject will be analyzed together with the pre-dose baseline sample. If a sample tests positive for anti-drug antibodies, the other samples from the subject will be analyzed to determine when antibodies developed. Serum samples which test positive for binding antibodies will subsequently be tested for neutralizing activity. Blood serum for ADA tests will be collected at screening, at the visit 4 weeks after treatment and at the end of cycle visit for each treatment cycle and will be stored for future analysis should the need arise, based upon the presence of ADA at the end of the study. Sample storage at -80°C is preferable, but samples can be stored at -20°C at sites if -80°C storage is not available. Samples will be stored (at completion of the trial and will be destroyed thereafter.

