3.3 Study Treatments and Assessments

Subjects will participate in this study for a duration of 50 to 62 weeks from signing the informed consent form (ICF) to the End of Study visit (i.e., up to 14 calendar days for screening, followed by 48 to 60 weeks study participation).

Subjects will receive a maximum of four permitted rounds of treatment, with a minimum interval between treatments of 12 weeks.

The first treatment cycle of the study will comprise of two treatment groups as follows:

- Group A (active): BoNT/A-DP (20 units, 0.5 mL).
- Group B (placebo control): sterile, 0.9% sodium chloride (0.5 mL).

An interim analysis (IA) will be performed when all subjects complete the re-evaluation for retreatment visit at week 16 of the first treatment cycle or complete the double blind phase (whichever occurs earlier). Refer to Section 8.9 for more details regarding the IA.

Eligible subjects will be randomized at baseline (day 0) to Group A or B to receive the first treatment in a 3:1 randomization scheme, respectively. Investigators and subjects will be blinded to the treatment administered and will evaluate the severity of glabellar lines independently. The subjects must perform their assessment independently and ideally before the investigator, to ensure they are not biased by the investigator. The same investigator must assess the subject at baseline and at the visits at weeks 1, 2 and 4 in the first treatment cycle.

After a screening period of up to 14 calendar days, subjects will receive the first treatment (BoNT/A-DP or placebo) and attend for visits at 1, 2 and 4 weeks after treatment and at 4-

Statistical Analysis Plan (SAP)

CROMA
est. 1976

weekly intervals thereafter for evaluation of efficacy and safety (primary and key secondary efficacy endpoints will only be evaluated in the first treatment cycle in comparison with placebo). Re-screening will not be permitted.

The effect of botulinum toxin typically lasts a few months, hence the first treatment cycle will last at least 12 weeks and will end when the subjects qualify for re-treatment.

Open Label Extension

After the first treatment cycle is completed, all subjects may enter the open label extension phase and will be dosed with BoNT/A-DP (20 U) for subsequent re-treatments.

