If at an Evaluation for Re-treatment visit the subject wants to get re-treated, but the investigator does not agree or vice versa (i.e., the FWS score is not \geq at least 2 by both assessments), the subject will return to the site four weeks thereafter for another Evaluation for Re-treatment visit. There is no limit to the number of Evaluation for Re-treatment visits. In order to consider a visit as the End of Cycle visit, there must always be agreement between investigator and subject on a FWS score (at maximum frown) of ≥ 2 .

End of Study Visit

The End of Study visit can take place in four-weekly intervals from study-week 48 until study-week 60. The last study drug re-treatment will be administered no later than week 48. For subjects receiving a re-treatment at week 48, the last cycle will end 12 weeks later at week 60 (i.e., End of Study visit).

The End of Study visit will take place at week 48 if the week 48 visit is an Evaluation for Re-treatment visit and the subject does not meet the criteria for re-treatment in case this visit is 12 or more weeks after the last treatment. As week 48 is the last possible time point for re-treatment, such subjects will continue with all additional assessments of the End of Study visit on the same day. For subjects having received their last injection eight weeks or less prior to week 48, the End of Study visit will take place 12 weeks after the last study drug treatment was given, e.g. week 52 if the subject was re-treated at week 40.

For subjects who are prematurely discontinued from the study (at any time), the End of Study visit will take place within one week of discontinuation.

A detailed description of procedures and assessments to be conducted during this study is summarized in the Scheduled of Study Assessments in Table 1 below.

COVID-19 Pandemic

Due to the COVID-19 pandemic, which touched the world mainly the first 6 months of 2020, it has been allowed that visits were done remotely instead of physically when site was closed.

All re-treatments were put on hold between the 16th March and 5th May 2020 due to concerns that the subject will not be able to return for Week 1 and Week 4 assessments. Consequently, when a subject was eligible for re-treatment at a visit, the injection has been delayed until the subject could go back to site (if the injection is done before or at Week 48).

	Statistical Analysis Plan (SAP)	croma est. 1976
---	--	---------------------------

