4.4 Safety Endpoints

The safety endpoints of this study are:

1. Frequency, severity and causal relationship of AEs, Serious Adverse Events (SAEs) and Adverse Events of Special Interest (AESIs) during the entire study period.
2. Antibody formation, evaluation pre-dose before each treatment, at four weeks after each treatment and at the final study visit.
3. Safety assessments by evaluating hematology, clinical chemistry, vital signs and ECGs as per study schedule.

Statistical Analysis Plan (SAP)

CROMA
est. 1976

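### Antibody results are promised by treatment group and time point, but first-line testing covers only the baseline and last samples, so intermediate percentages, transient antibodies and the placebo column are not supported

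*SAP*

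**What the plan says.** - **Endpoint.** SAP 4.4 lists "Antibody formation, evaluation pre-dose before each treatment, at four weeks after each treatment and at the final study visit". Protocol 6.4.2.3 agrees.
- **Collection.** SAP 8.7.3 has serum drawn "at screening, at the visit 4 weeks after treatment and at the end of cycle visit for each treatment cycle". The schedule in Protocol 2.1 also lists an antibody test at End of Study.
- **Testing.** SAP 8.7.3 says that "initially only the last sample obtained from each study subject will be analyzed together with the pre-dose baseline sample". It continues: "If a sample tests positive for anti-drug antibodies, the other samples from the subject will be analyzed to determine when antibodies developed". Protocol 11.15.2 has the same rule and says that the collected serum "will be stored for future analysis should the need arise, based upon the presence of ADA at the end of the study".
- **Reporting.** SAP 8.7.3: "The presence of antibodies will be summarized by counts and percentages of subjects by treatment group and time point". It also plans counts over time for subjects with a positive sample.
- **Crossover and early exit.** SAP 3.3: "After the first treatment cycle is completed, all subjects may enter the open label extension phase". For subjects discontinued early, "the End of Study visit will take place within one week of discontinuation".
- **Attribution.** SAP 8.7.2 counts a crossed-over placebo subject's adverse events under placebo in cycle 1 and under BoNT/A-DP afterwards. SAP 8.7 adds a cycle 2 baseline for laboratory data, vital signs and ECG. SAP 8.7.3 has no equivalent for antibodies.

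**The concern.** The endpoint, the testing rule and the planned table describe three different things. The endpoint and table call for results at every scheduled sampling time. The testing rule gives results for all subjects at two times only; anything between is known only for subjects selected because they were positive.

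The safety programme is meant to support approval with long-term data over several cycles (SAP 2.2, objective 4). Protocol 4.4.2.1 and 4.4.2.2 sum up the two earlier studies by saying that no ADA developed. A table of zeros here could be read the same way, although the rule supports only a statement about the last sample. A column headed placebo would look like a control when most of its last samples come from people already given active drug.

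**Working it through.** **Plan's own figures.** The documents give no figure for the antibody analysis. The enrolment total used below reproduces: 300 / (1 − 0.15) = 352.9, so 353. At 3:1, placebo is 353 / 4 = 88.25, about 88.

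**1. Samples drawn and assayed first-line.** A subject with c cycles has 1 + 2c scheduled samples: screening, then week 4 and End of Cycle (or End of Study) in each cycle. Two are assayed.

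| Cycles | Samples | Assayed first-line | Share |
|---|---|---|---|
| 1 | 3 | 2 | 67% |
| 2 | 5 | 2 | 40% |
| 3 | 7 | 2 | 29% |
| 4 | 9 | 2 | 22% |

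A four-cycle subject has 8 post-baseline samples, of which 1 is assayed first-line.

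**2. Intermediate percentages.** At an intermediate visit let N subjects attend, k of them be assayed because their baseline or last sample was positive, and m be positive at that visit.
- m/k uses a denominator selected on the outcome and would normally be too high.
- m/N counts untested subjects as negative and cannot exceed the true proportion (taking the assay as accurate).

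The SAP does not choose between them, and neither estimates the proportion positive at that visit.

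**3. Transient antibodies.** A subject negative at baseline, positive after an early treatment and negative at the last sample triggers no further testing. If t is the share of responders who are negative again by the last sample, detected incidence = true incidence × (1 − t). The documents give no t. As a range, t = 0, 0.25, 0.50 and 0.75 would leave 100%, 75%, 50% and 25% detected.

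At the extreme, a subject who receives one injection and never qualifies for re-treatment has the End of Study visit, and so the deciding sample, at week 48 (SAP 3.3).

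**4. The placebo column.** Protocol 4.4.2.2 gives 160 active and 53 placebo subjects in the earlier US study (BLESS II), and 208 who received BoNT/A-DP in either phase. Table 4-2 lists that study with the same layout as this one. Crossed over: 208 − 160 = 48 of 53 = 90.6%. Applied here:
- last sample after BoNT/A-DP: 88.25 × 0.906 = about 80
- last sample on placebo only: 88.25 × 0.094 = about 8.

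The range for placebo-only is about 5 to 13: 94.4% crossover gives 4.9 and 85% gives 13.2. The first is the printed placebo completion rate for the double-blind phase of BLESS I (its count of 160 of 177 is 90.4%, giving 8.5). The second is 1 minus the planned drop-out rate.

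**5. What zero positives would show.** The exact two-sided 95% upper limit for 0 of n is 1 − 0.025^(1/n).

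| n | Upper limit |
|---|---|
| 5 | 52.2% |
| 8 | 36.9% |
| 13 | 24.7% |
| 88 | 4.1% |

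The last row is what the stored cycle 1 samples could give if assayed in all placebo subjects.

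**The case against.** Tiered testing is a legitimate choice, and several stronger readings fail.

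- A reader might infer that only two samples per subject are ever assayed. The word *initially* and the follow-up sentence rule this out: a positive subject has all samples tested, including a placebo subject's cycle 1 samples.
- A reader might infer that there is no placebo comparison, or that only cycle 1 drop-outs could supply one. Subjects who decline re-treatment, who never qualify by week 48, or who were eligible but never re-treated because of the 2020 hold (SAP 3.3) can also have a placebo-only last sample. Cycle 1 placebo serum is collected and stored, so the gap lies in testing. *Almost none* is accurate.
- A reader might infer that the result measures only persistence. A negative baseline with a positive last sample does show formation, and the stored samples then date it.

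Other points have weight. Counts over time for positive subjects are already planned, and baseline is already a row in the by-time-point summary. Safety variables are descriptive with no testing between groups (SAP 8.7), and nothing promises a controlled antibody comparison. SAP 6.1 assigns safety subjects by treatment actually received. The table templates are in a separate document and may show the number tested.

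These points narrow the concern without removing it. SAP 6.1 deals with treatment received that differs from the assignment; it does not say where a sample belongs after a planned crossover. No table shell can supply results for samples that were not assayed. Relabelling does not recover transient responses; it only stops the report from implying that they were looked for.

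**Conclusion.** The point holds as a conflict between the endpoint (SAP 4.4), the testing rule and the planned summary (both SAP 8.7.3). Followed as written, the plan cannot give valid percentages at intermediate times, does not detect antibodies that clear before the last sample, and leaves almost no placebo comparison: about 8 of 88 subjects, range about 5 to 13, and a selected group.

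The placebo figures assume crossover like that in the earlier US study. The loss through transient responses cannot be sized, because the documents give no transient share. A reader might also infer that the earlier studies' reports of no ADA arose from the same rule; the documents do not describe the testing behind those statements.

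The impact is minor. The analysis is descriptive and does not touch the primary or key secondary results, but the mismatch is cheap to remove.

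**What to change.** In SAP 8.7.3 and the table shells:

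1. Give percentages only for baseline and for newly positive at the last sample. The denominators are the numbers tested: at baseline, and at both times for newly positive.
2. Attribute the last sample by actual exposure: placebo only, or any BoNT/A-DP, with the number of active treatments and the weeks since the last active injection.
3. Keep the planned counts over time for positive subjects, without percentages.
4. Label the result *ADA at last sample*, state that transient antibodies are not assessed, and align the wording of SAP 4.4.

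This costs SAP and table wording only, with no extra assays or blood draws. The downside is a narrower claim.

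Optional, and not needed for the fix: if a placebo-controlled figure is wanted, assay the stored cycle 1 End of Cycle samples in both arms, about 350 tests. That would still miss responses gone by the end of cycle 1 and transient responses in cycles 2 to 4.

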8.7.4 Laboratory Data

For the purposes of summarization in both the tables and listings, all laboratory values will be presented in SI units. If a lab value is reported using a nonnumeric qualifier e.g., less than (<) a certain value, or greater than (>) a certain value, the given numeric value will be used in the summary statistics, ignoring the nonnumeric qualifier.

Visit value and change and/or percent change from baseline (where applicable) during the treatment period will be summarized by treatment group using descriptive statistics for all laboratory parameters.

All laboratory values will be classified as normal or abnormal according to the central laboratory normal ranges and indicated as clinically significant (CS) or not clinically significant (NCS) by the investigator. Categorical variables will be summarized by counts and percentages of subjects in corresponding categories. Shift tables illustrating changes with respect to the central laboratory normal ranges and the investigator assessment between baseline and post-baseline visits will be created: number and percentage of subjects with normal, CS and NCS laboratory values.

Statistical Analysis Plan (SAP)

CROMA
est. 1976

8.7.5 Vital Signs

The analyses of variables for vital signs will focus on the evaluation of the change from baseline to the scheduled time points after baseline. Descriptive statistics by visit and of changes from baseline to each post-baseline visit by treatment cycle will be presented.

8.7.6 Electrocardiograms

Normal/abnormal shift tables illustrating changes between baseline and post-baseline visits will be created for the overall ECG interpretation by treatment group.

8.7.7 Physical Examinations

All physical examination data and abnormalities will be listed only.

8.8 Other Analysis

8.8.1 Subgroups

The following subgroup analyses will be performed for the primary efficacy endpoint. Subgroup analyses a) and b) will also be conducted for the key secondary efficacy endpoint and for the additional secondary efficacy endpoints ‘the percentage of responders at week 12 (after the first treatment)’, the percentage of responders at week 16 (after the first treatment)’, ‘the percentage of responders at week 20 (after the first treatment)’ and ‘the proportion of subjects with a ≥ 1 point reduction in FWS score at rest at week 4 in the first treatment cycle, based separately on the investigators’ and the subjects’ in-clinic assessments (applicable only for subjects who have a FWS score at rest ≥ 1 at baseline)’:

a) Subgroup analysis by site and country.

Subgroup analyses will be conducted by site and country. Sites with less than three placebo subjects will be combined. The χ^2 -test will be applied for each subgroup. In case of a total number of observations below 30, or in case of at least one cell frequency below 5, Fisher’s exact test will be used instead of the χ^2 -test. Stratified analyses applying the CMH test will also be conducted using factor country. 95% CIs will be presented, if applicable.

b) Subgroup analysis by subjects with previous use of botulinum toxin versus naïve subjects.

Subgroup analyses will be conducted for subjects with treatment with any serotype of botulinum toxin for any indication versus naïve subjects. The χ^2 -test or Fisher’s exact test (see above corresponding criteria to use Fisher) will be applied for each subgroup. No stratified analysis using factor pre-treated/naïve subjects is currently planned. 95% CIs will be presented, if applicable.

Statistical Analysis Plan (SAP)

CROMA
est. 1976

c) Subgroup analysis by race (American Indian or Alaskan Native, Asian, Black or African American, Native Hawaiian or Other Pacific Islander, Caucasian (Including Hispanic or Latino and Other)). The χ^2 -test or Fisher's exact test (see above corresponding criteria to use Fisher) will be applied for each subgroup. No stratified analysis using factor race is currently planned. 95% CIs will be presented, if applicable.

d) Subgroup analysis of:

- subjects with previous use of botulinum toxin by site
- naïve subjects by site

The χ^2 -test or Fisher's exact test (see above corresponding criteria to use Fisher) will be applied for each subgroup. No stratified analysis using site is currently planned. 95% CIs will be presented, if applicable.

e) Subgroup analysis by Fitzpatrick skin type (TYPE I, TYPE II, TYPE III, TYPE IV, TYPE V, and TYPE VI). The χ^2 -test or Fisher's exact test (see above corresponding criteria to use Fisher) will be applied for each subgroup. No stratified analysis using factor Fitzpatrick skin type is currently planned. 95% CIs will be presented, if applicable.

f) Subgroup analysis by sex. The χ^2 -test or Fisher's exact test (see above corresponding criteria to use Fisher) will be applied for each subgroup. No stratified analysis using factor sex is currently planned. 95% CIs will be presented, if applicable.

g) Subgroup analysis by ethnicity (Hispanic or Latino versus Not Hispanic or Not Latino). The χ^2 -test or Fisher's exact test (see above corresponding criteria to use Fisher) will be applied for each subgroup. No stratified analysis using factor ethnicity is currently planned. 95% CIs will be presented, if applicable.

h) Subgroup analysis by age groups (below 65 years, 65-74 years and 75-84 years). The χ^2 -test or Fisher's exact test (see above corresponding criteria to use Fisher) will be applied for each subgroup. No stratified analysis using factor age group is currently planned. 95% CIs will be presented, if applicable.

i) Subgroup analysis by additional age groups (below 65 years versus 65 years and older). The χ^2 -test or Fisher's exact test (see above corresponding criteria to use Fisher) will be applied for each subgroup. No stratified analysis using factor additional age group is currently planned. 95% CIs will be presented, if applicable.

Statistical Analysis Plan (SAP)

CROMA
est. 1976

Subgroups analyses will also be performed as follows for select additional secondary efficacy endpoints at select timepoints:

- The proportion of subjects with ≥ 1 point reduction in FWS score (at maximum frown) in the BoNT/A-DP and placebo groups during the first treatment cycle at week 4 relative to baseline, based on both the investigators' and the subjects' in-clinic assessments: all subgroups
- The proportion of subjects with ≥ 1 point reduction in FWS score (at maximum frown) in the BoNT/A-DP and placebo groups during the first treatment cycle at week 12, 16 and 20 relative to baseline, based on both the investigators' and the subjects' in-clinic assessments: by site, by country and by subjects with previous use of botulinum toxin versus naïve subjects.

Subgroup analyses will be performed on the FAS, MFAS and PP populations.

COVID-19 Pandemic:

Due to COVID-19 pandemic, the secondary endpoints 'the percentage of subjects with an improvement of ≥ 2 points in FWS at maximum frown at 4 weeks after re-treatment' and 'the percentage of subjects with ≥ 1 point reduction in FWS score at maximum frown at week 4 relative to re-treatment baseline' will be also analyzed using observed values by the FWS investigator assessment type (i.e. assessment done remotely or physically). The objective is to assess if the remote way has not impacted the investigator assessment.

These analyses will be performed for the final analysis.

Exclusion of Site 110 Subjects:

A site audit conducted in January 2019 as pointed out a critical finding on a protocol non-compliance: an unblinded site staff performed blinded tasks on safety assessments. In order to assess the impact on the results, analyses based on FAS for primary and secondary efficacy endpoints relative to the double-blind period of the trial will be repeated excluding all the subjects of the site 110.

AE summary tables for TEAEs and AESIs, and TEAEs and AESIs summarized by SOC, PT will be also repeated for each site and by excluding all the subjects of the site 110.

These analyses will be performed for the interim and final analyses.

Statistical Analysis Plan (SAP)

CROMA
est. 1976

ADA, laboratory, vital signs and ECG analyses will be also repeated by excluding all the subjects of the site 110 only for the final analysis.

Further analyses may be performed to assess the site 110 effect, if needed.

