4.2 Key Secondary Efficacy Endpoint

The key secondary efficacy endpoint of this study is:

1. The extent of change in psychological impact (emotional and social functioning and concerns relating to their glabellar lines) at week 4 after the first treatment, in the BoNT/A-DP group in comparison with placebo, relative to baseline, as assessed by the modified Skindex-16 (Glabellar Line Quality of Life Scale [GL-QoL]) and the FACE-Q (Appraisal of Lines Between Eyebrows and Age Appraisal visual analog scales (VAS)), respectively.

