8.6 Efficacy Analyses

8.6.1 Analysis Methods

The analyses of the primary and secondary outcome measures will be based on different statistical tests such as Cochran-Mantel-Haenszel (CMH) test, Pearson Chi-Square test, Wilcoxon Rank Sum test and Fisher's exact test, if appropriate. Details for each efficacy endpoint will be provided in the following sections. Subgroup analyses will be described in Section 8.8.1.

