8.6.3 Analysis of Secondary Efficacy Endpoints

The following order of tests will be defined for the analysis of the key secondary efficacy endpoint with multiplicity control as described in 8.6.1.1:

- Primary endpoint (composite endpoint)
- Key secondary endpoint 1
 - 1.1: The modified Skindex-16 (GL-QoL) Emotional domain
 - 1.2: The modified Skindex-16 (GL-QoL) Social Functioning domain
 - 1.3: The modified Skindex-16 (GL-QoL) Overall score
 - 1.4: The FACE-Q Appraisal of Lines Between Eyebrows scale
 - 1.5: The FACE-Q Age Appraisal VAS score

Analysis of key secondary efficacy endpoint 1: The extent of change in psychological impact (emotional and social functioning, and concerns relating to glabellar lines) at week 4 after

Statistical Analysis Plan (SAP)

CROMA
est. 1976

the first treatment, in the BoNT/A-DP group in comparison with placebo, relative to baseline, as assessed by the modified Skindex-16 (GL-QoL) and the FACE-Q Appraisal of Lines Between Eyebrows and FACE-Q Age Appraisal VAS.

The modified Skindex-16 (GL-QoL) and FACE-Q Appraisal of Lines Between Eyebrows scale and FACE-Q Age Appraisal VAS scales will be analyzed according to the foreseen analysis approach of these tools, as described below.

Emotional and Social Functioning

The modified Skindex-16 (GL-QoL) Emotional and Social Functioning domains and overall scores will be derived in accordance with the Skindex-16 manual, adapted for the GL-QoL. The scores will be standardized on a scale from 0 (no impact) to 100 (maximal impact); a scale score is the average of responses to items addressing a construct. Domain and overall scores will be calculated if at least two of three social and if at least two of four emotional domain items are present. Derivation details are included in Appendix B. The absolute change from baseline (measured on the screening visit) will be calculated for the domain and overall scores and statistically compared between the treatment groups using the Wilcoxon Rank Sum test or t-test, if appropriate. Estimates of ‘mild’, ‘moderate’, and ‘severe’ psychological impact, and of the minimal clinical important difference, will be used to aid interpretation of scores and will be considered exploratory.

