The analysis will be conducted with respect to the hierarchical order of the key secondary efficacy endpoint; the analysis using the Emotional domain first, the Social Functioning domain second, and the overall score third. All analyses will be conducted on observed values only, i.e., missing domain and overall scores will be excluded from analysis; no imputation of missing domain and overall scores will be performed.

Concerns Relating to Glabellar Lines

The FACE-Q Appraisal of Lines Between Eyebrows scale and FACE-Q Age Appraisal VAS scores will be derived in accordance with the developers’ instructions and missing data treated accordingly. The absolute change from baseline (measured on the screening visit) will be calculated for the FACE-Q Appraisal of Lines Between Eyebrows scale and for the FACE-Q Age Appraisal VAS score and statistically compared between the treatment groups using the Wilcoxon Rank Sum test. All analyses will be conducted on observed values only, i.e., missing scale scores will be excluded from analysis; no imputation of missing scores will be performed. This analysis will be conducted with respect to the hierarchical order of key secondary efficacy endpoints as well; the analysis of FACE-Q Appraisal of Lines Between Eyebrows scale first, followed by the analysis of FACE-Q Age Appraisal VAS scores.

Statistical Analysis Plan (SAP)

CROMA
est. 1976

Exploratory Analyses

Exploratory analyses of modified Skindex-16 (GL-QoL) domain and overall score and FACE-Q Appraisal of Lines Between Eyebrows scale and FACE-Q Age Appraisal VAS will also be conducted using the MFAS and PP populations. The analyses described in the two previous sections will be repeated for these populations.

In addition, shift tables tables will be produced displaying the Psychological Impact of Modified Skindex-16 (GLQoL) at baseline versus week 4. The FAS, MFAS and PP populations will be used.

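### SAP 8.8.1 names only tests for proportions (chi-square or Fisher) for the site, country and prior-toxin subgroup analyses of the key secondary endpoint, which is five change scores

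*SAP*

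**What the plan says.** SAP 4.2 defines the key secondary endpoint as "The extent of change in psychological impact (emotional and social functioning and concerns relating to their glabellar lines) at week 4 after the first treatment", relative to baseline and against placebo. SAP 8.6.1.1 splits it into five scores tested in fixed order: GL-QoL Emotional, Social Functioning and Overall (1.1 to 1.3), FACE-Q Appraisal of Lines Between Eyebrows (1.4) and FACE-Q Age Appraisal VAS (1.5). The first four are scored from 0 to 100, and the VAS runs from -15 to +15 (SAP 8.6.3 and Appendix C).

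SAP 8.6.3 takes the absolute change from the screening visit. Scores 1.1 to 1.3 are "statistically compared between the treatment groups using the Wilcoxon Rank Sum test or t-test, if appropriate". Scores 1.4 and 1.5 are "statistically compared between the treatment groups using the Wilcoxon Rank Sum test". It repeats these analyses for the MFAS and PP populations and does not mention subgroups.

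For subgroups, SAP 8.6.1 says "Subgroup analyses will be described in Section 8.8.1". That section opens by stating that "Subgroup analyses a) and b) will also be conducted for the key secondary efficacy endpoint", together with four additional secondary endpoints that are all proportions. Item a) (site and country) and item b) (previous toxin use versus naïve) prescribe a chi-square test in each subgroup. Fisher's exact test replaces it as follows: "In case of a total number of observations below 30, or in case of at least one cell frequency below 5". Item a) adds: "Stratified analyses applying the CMH test will also be conducted using factor country". Item b) plans no stratified analysis. Confidence intervals are promised only where applicable.

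The Key Secondary Analysis paragraph of the protocol synopsis has the same carry-over: the key secondary endpoint is to receive the analyses described for the binary primary endpoint. Protocol 12.4.2 lists the subgroups for these scores under Exploratory Analyses and names no subgroup test there.

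**The concern.** The methods in 8.8.1 a) and b) suit a responder endpoint. The scores have no responder cut-off in that section, so there is no 2 x 2 table to test. Followed as written, the rule cross-tabulates treatment against every distinct change value. Such a test asks whether the two distributions differ in any way, not whether BoNT/A-DP moved the score in the favourable direction. It also gives no treatment difference to compare between sites, countries or toxin strata, and that comparison is the purpose of a subgroup analysis.

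This is a stated rule that conflicts with 8.6.3, not a silence. The practical stakes are uninformative p-values for the quality-of-life scores by subgroup, or an unrecorded departure from the SAP if the programmer quietly uses Wilcoxon instead. Site-level results have some added interest here because 8.8.1 reports a critical audit finding at site 110.

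**Working it through.** **Plan's own figure.** The SAP gives no power or sample-size figure for any subgroup test. Its one power statement (SAP 5: primary endpoint, Fisher, one-sided 0.025, 46% versus 2%, 39 + 13 subjects, 92.3%) reproduces as 92.27% by exact enumeration. It does not bear on this point.

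**Subgroup sizes.** SAP 3.1 plans 353 subjects at about 7 sites: 353/7 = 50.4 per site, or about 38 versus 12 at 3:1. Half the trial is about 176, or 132 versus 44. This second size is an assumption, because the documents give no country or prior-toxin counts.

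**Which branch of the rule applies?** With 12 placebo subjects, at most two columns can hold five or more of them (12/5 = 2.4). Any site table with three or more distinct change values therefore has a cell below 5. With 44 placebo subjects the limit is eight columns (44/5 = 8.8). In the simulation below, a site table had about 14 to 15 columns and the 132:44 table about 18 to 19. Some cell was below 5 in every simulated table, so the switch to Fisher would be automatic. At site level about 94% of expected counts were below 5.

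**Order and direction.** Take change values -25, -12.5, 0, +12.5, with active counts 10, 10, 12, 6 (n = 38) and placebo counts 1, 2, 5, 4 (n = 12). Column totals are 11, 12, 17, 10. Expected placebo counts (12/50 of each total) are 2.64, 2.88, 4.08, 2.40; expected active counts are 8.36, 9.12, 12.92, 7.60.

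- Placebo contributions: 1.019 + 0.269 + 0.207 + 1.067 = 2.562
- Active contributions: 0.322 + 0.085 + 0.066 + 0.337 = 0.809 (from unrounded terms)
- Chi-square = 3.37 on 3 df, p = 0.338

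| Column order | Chi-square p | One-sided Wilcoxon p |
|---|---|---|
| As given | 0.338 | 0.036 |
| Reversed | 0.338 | 0.966 |
| Shuffled | 0.338 | 0.643 |

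**Power (illustrative).** The documents give no SD for any of these scores. Assumptions for the Emotional domain: 4 items scored 0 to 4 (steps of 6.25 points), baseline sum about N(9, 3.5), week 4 sum = 9 + 0.5 x (baseline - 9) + N(0, 3.0) + shift, rounded and truncated to the scale. Before rounding and truncation, the SD of change is √[(0.5 x 3.5)² + 3.0²] = 3.47 items, and 3.47 x 6.25 = 21.7 points. Wilcoxon is one-sided at 0.025; chi-square and its permutation version (an exact test of the same kind as Fisher on a 2 x k table) are at 0.05. There were 300 simulated data sets at 38:12 and 1,000 at 132:44, so the Monte Carlo standard error is at most √(0.25/300) = 2.9 and √(0.25/1000) = 1.6 percentage points.

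| Size, shift | Wilcoxon | Chi-square | Exact |
|---|---|---|---|
| 38:12, none | 1.7% | 2.7% | 4.3% |
| 38:12, 12.5 better | 35% | 9% | 13% |
| 38:12, 18.75 better | 64% | 19% | 25% |
| 132:44, 12.5 better | 87% | 37% | not run |
| 132:44, 12.5 worse | 0% | 38% | not run |

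A second run (SD 22, 400 data sets per setting) gives, at 38:12 and true differences of 15, 20 and 25 points, 43%, 68% and 88% with Wilcoxon against 15%, 25% and 43% with the unordered exact test. Both runs assume nearly the same SD. Together they cover standardised differences from 12.5/21.7 = 0.58 to 25/22 = 1.14, and another SD would move the result along that range.

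**CMH by country.** For a responder endpoint each country gives a 2 x 2 table and the CMH statistics coincide, so the choice does not matter. For a score they differ. SAP 8.6.2 names the General Association statistic for the primary endpoint; carried over, it would ignore order. A row-mean-scores statistic with rank scores would respect it. SAP 8.8.1 names neither.

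**The case against.** The best reply is that the consequence is small. Everything outside the fixed-order tests is exploratory (SAP 8.6.1.1), and 8.6.3 already names the right tests, so a competent analyst would probably use them in subgroups too. That stands as a limit on importance. It does not remove the conflict: 8.6.1 sends subgroup methods to 8.8.1, and 8.6.3 extends its tests only to the MFAS and PP populations.

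Some stronger readings are tempting, and the documents do not support them:

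- **That the tests are invalid.** Null rejection at site level was 2.7% and 4.3% against a nominal 5%. The tests are unsuitable and weak, but they do not inflate false positives.
- **That these subgroups are the only consistency check on the scores.** SAP 8.6.3 also plans MFAS and PP repeats and shift tables of psychological impact, and 8.8.1 repeats the double-blind efficacy analyses without site 110.
- **That nobody could tell which arm improved.** SAP 8.1 summarises continuous variables by treatment group, and those summaries can show direction. The p-value cannot.
- **That the CMH analysis must ignore order.** It is under-specified, not necessarily wrong, and it is planned only in a).

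The scores are also bounded and discrete rather than strictly continuous. That does not rescue the chi-square test, because their values are still ordered.

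**Conclusion.** The mismatch is real and follows from the text alone: SAP 8.8.1 assigns tests for proportions to five change scores and names no suitable test for them. The lack of order and direction needs no distributional assumption, and neither does the automatic switch to Fisher once a site has three or more distinct change values. The power loss does need one. Under an assumed SD of about 22 points, the unordered tests have roughly a quarter to a half of the Wilcoxon power at one site. That figure is illustrative, was simulated for a 4-item score only, and is not a forecast for the other four scores.

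The effect is confined to exploratory results by site, country and previous toxin use. The primary endpoint, the fixed-order tests of 8.6.3, the alpha level and the sample size are untouched. The point is worth correcting because the correction is cheap and the rule as written serves no purpose for these scores.

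**What to change.** Add to SAP 8.8.1 a) and b):

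> For key secondary scores 1.1 to 1.5, the change from baseline (screening) is compared between treatment groups within each subgroup by the test used for that score in Section 8.6.3 (Wilcoxon rank sum, or t-test where 8.6.3 allows it). The estimated treatment difference and its 95% CI are presented. In a), the analysis stratified by country uses the van Elteren test or the row-mean-scores CMH statistic with rank scores.

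State that chi-square, Fisher and general-association CMH apply to the responder endpoints only. Align the Key Secondary Analysis paragraph of the protocol synopsis, which appears to be the source of the carry-over.

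The cost is a few lines of wording. The within-subgroup tests can reuse the 8.6.3 programs; the interval estimates and the ordered stratified test need a little extra programming. If the SAP can no longer be amended, the change should be described and justified in the clinical study report, as SAP 1 requires for deviations.
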